7.1 Assessment of Severity (Intensity)

The following definitions for rating severity (intensity) will be used:

Mild: A type of AE that is usually transient and may require only minimal treatment or therapeutic intervention. The event does not generally interfere with usual activities of daily living.

Moderate: A type of AE that is usually alleviated with specific therapeutic intervention. The event interferes with usual activities of daily living, causing discomfort but the subject is still able to function.

Severe: A type of AE that interrupts usual activities of daily living, or significantly affects clinical status, or may require intensive therapeutic intervention.

7.2 Assessment of Relationship to Study Drug

The Investigator will use his/her clinical judgment to explain each AE and determine its relationship, if any, to study drug treatment. Alternative causes, such as natural history of the underlying diseases, concomitant therapy, other risk factors and the temporal relationship of the event to the study drug will be considered and investigated. The Investigator will also consult the Investigator's Brochure in the determination of his/her assessment. Causality should be assessed using the following categories:

Not Related The event can readily be explained by factors not involving the study drug and a temporal relationship with the study drug does not exist.

Possibly Related There is some temporal relationship between the event and the administration of the study drug and the event is unlikely to be explained by the subject's medical condition or other therapies.

Probably Related The temporal relationship between the event and the administration of the study drug is suggestive, and the event is less likely to be explained by the subject's medical condition or other therapies.

Definitely Related The event follows a reasonable temporal sequence from administration of the study drug, follows a known or suspected response pattern to the study drug, was confirmed by improvement upon stopping the study drug

(dechallenge) and reappears upon repeated exposure (rechallenge). Note: this is not to be construed as requiring re-exposure of the subject, however, a category of definitely related can only be used when recurrence is observed.

7.3 Serious Adverse Events

An SAE is any untoward medical occurrence that:

- Results in death
- Is life-threatening
- Results in persistent or significant disability/incapacity
- Requires in subject hospitalisation or prolongation of existing hospitalisation
- Is a congenital anomaly/birth defect
- Is an important medical event

NOTE: medical or scientific judgment should be exercised in deciding whether reporting is appropriate in other situations, such as important medical events that may not be immediately life threatening or result in death or hospitalisation but may jeopardise the subject or may require medical or surgical intervention to prevent one of the other outcomes listed in the above definition. These should also be considered serious. Examples of such events are invasive or malignant cancers, intensive treatment in an emergency room or at home for allergic bronchospasm, blood dyscrasias or convulsions that do not result in hospitalisation or development of drug dependency or drug abuse.

All SAEs for subjects occurring from the time of informed consent through to the follow-up visit must be reported to Panoptes Pharma GesmbH or their representative within 24 h of the knowledge of the occurrence (this refers to any AE that meets one or more of the aforementioned serious criteria).

The SAE form should be completed in as much detail as possible but a lack of complete information should not delay the reporting of the SAE.

There may be situations when an SAE has occurred and the Investigator has minimal information to include in the initial report to the Clinical Trials Coordination Centre, Medical University of Vienna. However, it is very important that the Investigator always makes an assessment of causality for every event prior to transmission of the SAE report form to Clinical Trials Coordination Centre, Medical University of Vienna. The Investigator may change his/her opinion of causality in light of follow-up information, amending the SAE report form accordingly. The causality assessment is one of the criteria used when determining regulatory reporting requirements.

The Investigator will provide the assessment of causality as per instructions on the SAE

If an SAE occurs during this study, the following (Sponsor) personnel should be contacted:

Clinical Trials Coordination Centre, Medical University of Vienna:
[contact]

Panoptes Pharma:

[name]:

Phone (office and after-hours): [name]

7.4 Other Reportable Events

Certain events that occur in the absence of an AE should be reported to the Sponsor as Other Reportable Events. These include the following:

- Pregnancy exposure (subject becomes pregnant while taking study drug)
 - Subjects who are pregnant at Screening are not permitted to take part in this study; however, Panoptes Pharma GesmbH or their representative must be notified of any subjects that become pregnant while participating in this study (or the partner of a male subject). Although pregnancy is not technically an AE, all pregnancies must be followed to conclusion to determine their outcome. This information is important for both drug safety and public health concerns. It is the responsibility of the Investigator or designee to report any pregnancy in a subject that occurs during this study to Panoptes Pharma GesmbH or their representative.
- Lactation exposure (subject is taking study drug while nursing an infant)
- Accidental exposure (someone other than the study subject is exposed to study drug)
- Overdose (subject receives more than the prescribed dose of study drug within a given timeframe)
- Other medication errors that potentially places subjects at a greater risk of harm than is previously known or recognised (e.g., study drug is administered by an incorrect route)

8. DRUG SUPPLIES

8.1 PP-001

PP-001 is formulated as sterile, ophthalmic formulation (eye drop formulation) at three different strengths (3.0, 1.5 and 0.5 mg/ml). Sodium chloride, sodium hydroxide, hydrochloric acid, human serum albumin (HSA) and water for injection are added as excipients. The formulation does not contain preservative agents. Final dosage forms were prepared by diluting a concentrate formulation (5.0 mg/ml) of the highest technically feasible PP-001 concentration in this composition with vehicle solution. As primary package material, sterile 10 ml LDPE dropper bottles are used. Filling volume of each bottle is 3 ml. An overview on the composition of the formulation and a description of the function of the ingredients is given below in Table 5.

Table 5: Qualitative composition of PP-001 eye drop formulation

Component	Function	Reference to Quality Standards
PP-001	Active ingredient	In-house specification
Human serum albumin*	Solubilizing agent	Ph. Eur.
Sodium chloride	Tonicity adjustment	Ph. Eur.
Sodium hydroxide	pH adjustment, deprotonation, solubilizing agent	Ph. Eur.
Hydrochloric acid	pH adjustment	Ph. Eur.
Water for injection	Solvent	Ph. Eur.

*Albunorm 20%®; diluted to 5% final concentration

8.1.1 Packaging and Labelling

Study drugs will be packaged and labelled in accordance with the applicable regulatory authority requirements.

8.1.2 Storage of Study Drugs

Access to all study drugs must be restricted to designated study personnel throughout the study.

PP-001 will be stored between 15 and 25°C.

8.1.3 Product Accountability

The Investigator is responsible for study medication accountability, reconciliation and record maintenance. In accordance with all applicable regulatory requirements, the Investigator or designated study site personnel must maintain study drug accountability records throughout the course of the study. This person(s) will document the amount of study drug received from the supplier, the amounts dispensed to subjects as well as lot numbers and expiration/retest date of study medications.

At the conclusion of the study, any unused study drug will either be returned to a Sponsor-designated recipient or destroyed at the site after discussion with the Sponsor. If no supplies remain, this will be recorded in the drug accountability section of the final monitoring report.

All unused study drug provided by the Sponsor will be retained for purposes of drug accountability. In addition, empty and partially used bottles of PP-001 will be retained by the pharmacy for the purposes of drug accountability. Every effort will be made to retain used containers of PP-001 in the pharmacy for the purposes of drug accountability.

A member of the Sponsor's clinical operations staff (or designee) will check the supplies storage, dispensing procedures and records at regular intervals throughout the study.

The unit of accountability will be one bottle of eye drops.

9. STATISTICAL ANALYSIS

Statistical analyses of the primary and secondary outcomes will be conducted as outlined below. Descriptive statistics, including the numbers and percentages for categorical variables, and the numbers, means, standard deviations, medians, minimums, and maximums for continuous variables will be provided. Additional statistical analyses, other than those described in this section, may be performed if deemed appropriate. A description of the statistical analysis performed on the study data will be outlined in the Statistical Analysis Plan.

9.1 Treatment Comparison of Interest

A comparison will be made between the cohorts with regard to safety and tolerability.

9.2 Sample Size Determination

Twenty-four healthy female or male subjects will be enrolled in cohorts 1-3. Twenty-one subjects will be enrolled in cohort 4. No power calculations have been performed and the sample size is based on the requirements of the study design.

9.3 Analysis Populations

9.3.1 Intent-to-Treat Analysis Set

The Intent-to-treat (ITT) Analysis Set will consist of all subjects regardless of whether or not the subject received study drug.

9.3.2 Per-protocol Analysis Set

The Per-protocol Analysis Set will consist of all ITT Analysis Set subjects who have no major protocol deviations and who complete the study up to the end of the post-study assessments.

9.3.3 Safety Analysis Set

The Safety Analysis Set will consist of all subjects who receive any amount of study drug. All safety analyses will be conducted in this population.

9.3.4 Pharmacokinetic Analysis Set

All subjects in cohorts 1-3 who receive any amount of study drug will be included in the formal analysis of pharmacokinetic parameters providing they have at least one evaluable pharmacokinetic sample.

9.4 Criteria for Evaluation

9.4.1 Safety Analysis Variables

Safety parameters (i.e., changes in clinical signs and symptoms from physical exam, changes in clinical laboratory parameters, vital signs and AEs).

9.4.2 Pharmacokinetic Analysis Variables

The concentration of PP-001 in plasma at predose, postdose (30 min and 1h \pm 5 minutes after dosing), day 8 and day 19 (30 min \pm 5 minutes after last dosing of the day) will be determined (cohorts 1-3 only).

9.5 Demographic and Baseline Characteristics

Enrolment, protocol deviations and discontinuations from the study drug and the study will be summarised. Demographics (age, race, ethnicity and sex), medical and surgical history and study drug administration will also be summarised by treatment group.

9.6 Safety Analysis

Safety will be evaluated in the Safety Analysis Set by presenting summaries of AEs and vital signs.

Summary tables will be provided for all treatment-emergent AEs (TEAEs). A TEAE is defined as an AE with a start date and time on or after the first dose of study drug. Adverse events will be coded using the Medical Dictionary for Regulatory Activities (MedDRA®). The number and percentage of subjects with TEAEs will be tabulated by system organ class and MedDRA Preferred Term for each treatment group and by severity and relationship to treatment.

Adverse events leading to premature discontinuation from the study drug and serious TEAEs will be presented either in a table or a listing.

Descriptive statistics of vital signs and the change from baseline for each scheduled evaluation will be summarised at each study visit and the worst overall post-baseline value will be provided. The number and percent of subjects with treatment-emergent values with potential clinical significance will be tabulated.

Descriptive statistics of laboratory parameters and the change from baseline for each scheduled evaluation will be summarised at each study visit. The number and percent of subjects with treatment-emergent values of potential clinical significance will be tabulated by parameter.

9.7 Pharmacokinetic Analyses

The concentration of PP-001 in plasma will be measured in blood samples from subjects of cohorts 1-3, taken at pre-dosing, 30 min and 1h post-dosing and on day 8 and day 19 at 30 min after the last administration of the day. The PP-001 concentrations in plasma will be listed, graphed, and summarized by time point, day and treatment group.

Descriptive statistics for the PK parameters will include mean, standard deviation, coefficient of

variation, geometric mean, CV% geometric mean, median, min and max. When a geometric mean will be presented, it will be stated as such.

9.8 Handling of Missing Data

Missing values will not be imputed.

9.9 Interim Analysis

Cohorts 1 to 3 will be performed in dose ascending order. On the first two study days in Part I of each cohort, one subject will be dosed per day. On the third study day up to two subjects can be dosed per day. On the following study day(s) up to 4 subjects can be dosed per day. Randomization will be performed in two blocks (3:1, PP-001 vs. placebo) for each cohort. Part II will start at least 7 days after the last subject has been dosed in Part I and the Principal Investigator and the sponsor decide whether or not to continue dosing the cohort in Part II. The DSMB will decide if the safety and tolerability demonstrated in Parts I and II of the previous cohort warrant continuing the study at the next highest dose.

10. STUDY MONITORING

10.1 Clinical Monitoring

All aspects of the study will be carefully monitored by the Sponsor's authorised individuals, acting as agents of the sponsor with respect to current GCP and Standard Operating Procedures for compliance with applicable government regulations. These individuals will have access to all records necessary to ensure integrity of the data and will periodically review the progress of the study with the Investigator.

Frequent communication between the study site and the Sponsor is essential to ensure that the subject safety is monitored adequately. The Investigator will make safety assessments on an ongoing basis. The Sponsor's medical monitor will review safety information from all study sites as it becomes available throughout the study.

10.2 Data Safety Monitoring Board

Safety will be assessed by monitoring the results of the ophthalmic examinations and AEs throughout the study. Risk assessments will be made by the DSMB after each cohort 1-3 in written form and throughout the study based on the above. For details please refer to the DSMB charter.

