2.3 Primary Endpoint

The primary endpoint will be safety and tolerability as assessed through:

- Adverse events
- Serious AEs (SAEs)
- Laboratory safety tests
- Concomitant medication
- Vital signs
- Physical examination

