7. ADVERSE EVENTS

An AE is any untoward medical occurrence in a patient or clinical investigation subject administered a pharmaceutical product that does not necessarily have a causal relationship with this treatment. An AE can therefore be any unfavourable and unintended sign (including an abnormal laboratory finding), symptom, or disease temporally associated with the use of an IP, whether or not related to the IP.

Any pre-existing conditions or signs and/or symptoms present in a subject before the start of the study (i.e., before informed consent) should be recorded as medical/surgical history. Any medical occurrences that are new or worsened from the time of informed consent and up to and including the final visit must be reported as AEs or SAEs. All AEs and SAEs must be recorded irrespective of whether they are considered drug-related.

Subjects will be monitored throughout the study for adverse reactions to the study medications and/or procedures at each study visit. Questions will be posed in a non-leading manner so as not to bias the response. In addition to questioning at specific time points, subjects will be encouraged to report any AEs spontaneously. Subjects will also record any AEs occurring during the outpatient phase in a subject diary card. Any subject with an AE, SAE or clinically significant abnormal laboratory test value will be evaluated by the Investigator, or a monitoring physician, and will be treated and/or followed up until the symptoms or values have resolved or are assessed as stable by the Investigator. A physician, either at the Investigative site or at a nearby hospital emergency room, will administer treatment for any SAEs. Where appropriate, medical tests and examinations may be performed to ensure that an AE has fully resolved.

Adverse events and SAEs will be monitored throughout the study from the time a subject provides consent through to the final follow-up visit. Whenever possible, a specific disease or syndrome rather than individual associated signs and symptoms should be identified by the Investigator and

recorded on the subject's eCRF. However, if an observed or reported sign or symptom is not considered a component of a specific disease or syndrome by the Investigator, it should be recorded as a separate AE on the subject's eCRF.

Each AE or SAE reported will be assessed for severity and the date and time of onset (if available), relationship to dosing, duration and outcome of each event will be noted.

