Laboratory abnormalities are not considered AEs unless they are associated with clinical signs and symptoms or require medical intervention.

The Investigator will exercise medical and scientific judgment in deciding whether an abnormal clinical laboratory finding or other abnormal assessment is clinically significant.

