6.2 Laboratory Parameters

The following information will be analyzed descriptively and corresponding details on the subject level will be provided in data listings:

- Laboratory results

Laboratory results for the different laboratory parameters will be shown by time point.

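### Without declaring it, the SAP drops the protocol's change-from-baseline and flagged-value tables for laboratory tests and vital signs, and the stated DSMB basis names neither

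*Protocol*

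**What the plan says.** **Endpoint.** Protocol 2.3 lists "Laboratory safety tests" and vital signs as components of the primary endpoint. SAP 1.3.1 keeps both.

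**Planned analysis in the protocol.** For laboratory parameters, protocol 9.6 asks for visit summaries with change from baseline, and adds: "The number and percent of subjects with treatment-emergent values of potential clinical significance will be tabulated by parameter". For vital signs it asks for the same and for the worst post-baseline value. The synopsis repeats the vital-sign count. Protocol Appendix 2 supplies limits.

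**Planned analysis in the SAP.** SAP 6.2 describes laboratory data in one line: "Laboratory results for the different laboratory parameters will be shown by time point". Table 4.7 is the only laboratory table in SAP 7.1, and Listing 4.3 gives subject-level results. SAP 6.3 places vital signs among items that are listed only (Listing 4.4), and SAP 7.1 has no vital-sign table. SAP 2.11 reports one change to endpoints or analyses, the removal of concomitant medication from the primary endpoint. It says nothing about these outputs.

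**DSMB.** Protocol 10.2 opens: "Safety will be assessed by monitoring the results of the ophthalmic examinations and AEs throughout the study". It continues: "Risk assessments will be made by the DSMB after each cohort 1-3 in written form and throughout the study based on the above". Details are left to the charter.

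**AE status.** The opening definition in protocol section 7 lets an AE be "any unfavourable and unintended sign (including an abnormal laboratory finding" and so on. Later in the same section: "Laboratory abnormalities are not considered AEs unless they are associated with clinical signs and symptoms or require medical intervention".

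**The concern.** Two components of the primary endpoint lose analyses that the protocol promised, and the reader of the SAP is not told. In groups of 6 and 14 active subjects, how many subjects crossed a limit is the natural summary of a safety measurement, because a mean can hide one affected subject.

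The monitoring text has a gap at the same place. Laboratory abnormalities without symptoms or intervention are outside the AEs under the later statement in section 7, and 10.2 builds the DSMB assessment on AEs and eye examinations. Cohort 4 has no pharmacokinetic sampling and an ECG only at screening (protocol Table 2), so laboratory values and vital signs are among the few systemic safety data in the patient cohort.

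**Working it through.** **1. Is there a figure to reproduce?** No. Protocol 9.2 states: "No power calculations have been performed and the sample size is based on the requirements of the study design". The design counts add up: 3 × (6 + 2) = 24 and 14 + 7 = 21. The rest is a comparison of texts.

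**2. Outputs side by side.**

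| Output | Protocol 9.6 | SAP, laboratory | SAP, vital signs |
|---|---|---|---|
| Summary by visit | both | Table 4.7 | none |
| Change from baseline | both | not named | none |
| Worst post-baseline value | vital signs | not required | none |
| Count and percent flagged | both | none | none |
| Subject listing | not specified | Listing 4.3 | Listing 4.4 |
| Declared in SAP 2.11 | – | no | no |

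**3. What the remaining laboratory table can show.** Appendix 2 sets limits for 4 haematology + 15 chemistry + 2 urinalysis = 21 laboratory parameters. SAP 2.4 defines summaries as n, mean, SD, median, quartiles, minimum and maximum, so an extreme value shows as a maximum or minimum. It does not show how many subjects crossed a limit. By my count, 12 of the 21 limits are relative to the reference range (for example AST, ALT, sodium), 2 differ by sex (haemoglobin, haematocrit) and 7 are fixed: 12 + 2 + 7 = 21. For the first 14, a group maximum alone does not settle whether a limit was crossed. The blood-pressure limits are changes from baseline (systolic over 30 mmHg, diastolic over 20 mmHg), so a listing of values leaves the reader to work out each flag.

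**4. Size of one affected subject.** A shift of d in one subject moves a group mean by d/n: d/6 = 0.167d in a healthy cohort and d/14 = 0.071d in Cohort 4. As a count, the same subject is 1/6 = 16.7% or 1/14 = 7.1%.

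**5. How often would there be something to count?** The documents give no rate, so p is assumed. The chance of at least one affected active subject is 1 − (1 − p)^n:

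| Assumed p | n = 6 (one healthy cohort) | n = 14 (Cohort 4) | n = 18 (Cohorts 1–3, if full) |
|---|---|---|---|
| 5% | 26.5% | 51.2% | 60.3% |
| 10% | 46.9% | 77.1% | 85.0% |
| 20% | 73.8% | 95.6% | 98.2% |

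SAP 2.11 says Cohort 3 stopped early, so the last column is an upper bound.

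**6. Following one value through the plan.** Take a laboratory value that the investigator rates clinically significant, with no symptoms and no intervention.
- *AE?* The opening definition in section 7 allows it; the later statement excludes it.
- *Followed up?* Yes. Protocol 6.1.5 has it repeated and tracked to resolution, section 7 requires evaluation of the subject, and 10.1 has the sponsor's medical monitor review safety information.
- *To the DSMB?* Not on the basis stated in 10.2, unless the investigator raises it as a major safety concern (6.8.3) or the charter provides for it.
- *In the report?* In Listing 4.3 and inside the Table 4.7 summary, but in no count.

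The laboratory exclusion in section 7 does not apply to vital signs. An abnormal vital sign can be an AE in the ordinary way, but 10.2 does not name vital signs either.

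**7. Timing.** In protocol Table 2 the only full laboratory panel after dosing starts is on Day 13, and dosing ends on Day 11: 13 − 11 = 2 days later (window ±1 day). In Table 1 it is Day 21, after dosing ends on Day 19. Flagged laboratory values therefore inform decisions about later subjects, not that subject's own dosing. Vital signs are taken during dosing.

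**The case against.** The strongest reply is that nothing is hidden. Summaries carry the maximum, each subject's result is listed, and the groups are small enough to read by eye. Clinically significant values are graded and followed whether or not they are AEs. This stands. A reader might infer that a primary safety endpoint can escape review; the documents do not support that.

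On the DSMB, the charter was not available and may list laboratory data. Elsewhere the board judges safety and tolerability, which protocol 2.3 defines to include laboratory tests and vital signs, and protocol section 3 refers to the safety data of Cohorts 1–3. This also stands: one cannot conclude that the DSMB was denied laboratory data or that doses were escalated without them. Still, where 10.2 sets out the basis of the risk assessments, it omits both.

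A third reply is that the SAP only elaborates the protocol (SAP 2.1), so 9.6 still applies. This is weaker. SAP 7.1 is the list of tables to be produced, the notes in SAP section 7 illustrate splitting and relabelling but not added analyses, and SAP 6.3 explicitly assigns vital signs to listings.

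Two limits are accepted. A laboratory abnormality that needs intervention remains an AE even without symptoms. And declaring every clinically significant value an AE would be a reporting preference, not the correction of an error.

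**Conclusion.** The point holds as an undeclared departure of the SAP from protocol 9.6 on two primary-endpoint components, together with a gap in the stated basis of DSMB review. For laboratory data the flagged counts and change from baseline are missing; for vital signs every planned summary is missing. Counts against 21 laboratory limits and the vital-sign limits have no planned output.

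The consequence is moderate. The values are collected, followed and listed, so what is lost is the summary and an assured route to the DSMB, not the data. The SAP part affects all four cohorts. The DSMB part can now change conduct only in Cohort 4, because SAP 2.11 places the end of Cohort 3 before Cohort 4 began.

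This rests on reading SAP 7.1 as the full list of tables, on the protocol text in the absence of the charter, and, for the probabilities only, on assumed rates of 5% to 20%. The AE wording in section 7 needs reconciling whichever way the sponsor decides.

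**What to change.** 1. **SAP 6.2, 6.3 and 7.1:** add the protocol 9.6 tables for laboratory parameters and vital signs: change from baseline by visit, the worst post-baseline value for vital signs, and the number and percent of subjects crossing Appendix 2 limits. Define baseline for each. Screening is the only full laboratory panel before dosing, whereas vital signs are taken at screening and on Day 0. State how the heart-rate limits apply, since Appendix 2 gives them for supine and erect posture and protocol 6.1.2 measures seated subjects. If any table is not to be produced, declare and justify that in SAP 2.11.
2. **Protocol 10.2:** name, among the data given to the DSMB, laboratory and vital-sign values that cross Appendix 2 and laboratory values rated clinically significant. Keep this consistent with the charter.
3. **Protocol section 7:** reconcile the two statements on when a laboratory abnormality is an AE.

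The cost is one or two extra tables, a few sentences and slightly more DSMB material. The values are already collected, and investigators already rate laboratory results for clinical significance.
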